#### **8.4.4 Secondary Efficacy Analysis**

The secondary endpoint defined as the proportion of patients who maintain GH response will utilize the same methods as outlined above for the primary endpoint. Analyses will be presented using both the FAS and the PP analysis set. For the analysis of the proportion of responders based on mean GH, only patients with a screening mean GH value of  $< 2.5$  ng/mL will be included in the analysis. The time to loss of response will be summarized using the Kaplan-Meier method, and treatment groups will be compared using a Log-Rank test. The proportion of patients who begin rescue treatment prior to and including week 36 will be compared using Fisher's exact test. The denominator for each group will be all patients randomized to that group. The numerator will be those who start rescue treatment prior to and including week 36.

After the study is completed, if there is an imbalance in any baseline characteristics felt to be clinically meaningful, the effect of this imbalance on the secondary endpoints will be evaluated through inclusion of covariates for these characteristics into the models described above. These analyses will be considered sensitivity analyses to investigate the robustness of the primary analyses for the secondary endpoints.

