### 3.1 Randomization

Eligible subjects will be randomized 1:1 to octreotide capsules or placebo using permuted block randomization. Randomization will be stratified by prior SRL dose (Low vs Middle or High)

SRL Injection Dose	Dose Level Category
Octreotide dose of 10 mg q4w Lanreotide dose of 60 mg q4w or 120 mg q8w	Low
Octreotide dose of 20 mg q4w Lanreotide dose of 90 mg q4w or 120 mg q6w	Middle
Octreotide dose of 30 mg q4w Lanreotide dose of 120 mg q4w	High

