### 3.2 Sample Size

Approximately 50 patients will be enrolled into the DPC period of the study on either octreotide capsules or matching placebo, in a 1:1 ratio.

[Redacted]	[Redacted]	[Redacted]
[Redacted]	[Redacted]	[Redacted]
[Redacted]	[Redacted]	[Redacted]
[Redacted]	[Redacted]	[Redacted]
[Redacted]	[Redacted]	[Redacted]
[Redacted]	[Redacted]	[Redacted]
[Redacted]	[Redacted]	[Redacted]
[Redacted]	[Redacted]	[Redacted]

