### **6.3.5 Multiplicity**

As there is a single primary endpoint, with a single primary hypothesis test, no adjustment for multiplicity is needed for the primary endpoint/hypothesis test.

To adjust for multiplicity among the secondary endpoints, a fixed testing order will be used. The secondary endpoints will be tested in the pre-specified order as outlined in section 5.1.2, if the primary endpoint is found to be statistically significant. Testing will proceed to the next endpoint if the preceding endpoint is found to be statistically significant at the 5% (two-sided) level. The moment an endpoint is found not to be significant at the 5% (two-sided) level, all remaining endpoints will be considered exploratory, instead of confirmatory. No adjustment for multiplicity will be made for the exploratory endpoints.

The OLE period is viewed as a sub-study. No adjustment for multiplicity for the OLE endpoints will be made.

There will be no statistical analyses of baseline characteristics, demographics or safety endpoints.

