## 6.8.2 Secondary Endpoint Analyses

Analyses will be presented using both the FAS and the PP analysis set.

For the analysis of the proportion of responders based on mean GH, only patients with a screening mean GH value of  $< 2.5$  ng/mL will be included in the analysis. GH response will be defined using the mean integrated GH value, based on 5 assessments, 30 minutes apart. Patients who discontinue treatment during the DPC period for any reason will be classified as non-responders for the GH response analysis, regardless of their GH values. If a patient is missing their week 36 mean integrated GH value, this value will be imputed using the the Markov Chain Monte Carlo (MCMC) method for multiple imputation as outlined above. The adjusted proportions will be obtained from an exact logistic regression model, with covariates for treatment, baseline SRL dose (low vs mid or high) and baseline GH level ( $<$  median vs  $\geq$  median). The adjusted proportions, difference in proportions and associated two-sided 95% confidence intervals will be reported. In addition, the odds ratio and two-sided 95% confidence interval (CI) will be reported.

The time to loss of response will be summarized using the Kaplan-Meier method, and treatment groups will be compared using a Log-Rank test. Time zero is defined as the date time of the first dose of study medication. For each time to loss of response endpoint, three different analyses will be reported, with each of the three different analyses using a different approach (as defined earlier) to account for patients who discontinue from the study prior to meeting the definition of loss of response.

A Fisher's Exact Test will be used to compare the proportion of patients who begin rescue treatment prior to and including week 36. The denominator for each group will be all patients randomized to that group. The numerator will be those who start rescue treatment prior to and including week 36. The proportions within each treatment group, difference in proportions and exact two-sided 95% confidence interval will be reported.

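### Rescue endpoint: Fisher's test is valid but conservative at about 25 per arm. An exact unconditional test never rejects less, and the unnamed exact interval can disagree with the p-value in either direction

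*SAP*

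**What the plan says.** SAP 6.8.2 states that a Fisher's "Exact Test will be used to compare the proportion of patients who begin rescue treatment prior to and including week 36". For the denominators it says: "The denominator for each group will be all patients randomized to that group". For estimation it adds: "The proportions within each treatment group, difference in proportions and exact two-sided 95% confidence interval will be reported". It does not say how that exact interval is built.

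Protocol 8.4.4 agrees on the test: "The proportion of patients who begin rescue treatment prior to and including week 36 will be compared using" Fisher's exact test. The protocol synopsis says the same.

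Rescue is item 4, the last, in SAP 5.1.2. SAP 6.3.5 says "The secondary endpoints will be tested in the pre-specified order as outlined in section 5.1.2", and "Testing will proceed to the next endpoint if the preceding endpoint is found to be statistically significant at the 5% (two-sided) level". Rescue is therefore confirmatory only if the primary endpoint and the first three secondary endpoints all succeed, and no later test depends on it.

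On size, SAP 3.2 says: "Approximately 50 patients will be enrolled into the DPC period of the study on either octreotide capsules or matching placebo, in a 1:1 ratio". SAP 3.1 uses permuted blocks stratified by prior SRL dose (two strata), so an exact 25/25 split is likely but not assured. No rescue rate or power for this endpoint is readable; the sample-size tables are blacked out.

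**The concern.** Two things are at stake.

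- **Power.** Fisher's test conditions on the total number of patients rescued. The design fixes the arm sizes, not that total. With about 25 per arm the conditional distribution has few attainable p-values, so the true size falls well below 5%. An exact unconditional test can use more of the 5% without exceeding it.
- **Coherence.** A p-value from a conditional test will stand beside an exact interval for a difference in proportions, and that interval has no named construction. The two can point in opposite directions. Which direction arises would depend on a software default, perhaps chosen after unblinding.

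**Working it through.** **Inputs from the documents:** two-sided 5%; all randomized patients as denominator; about 50 patients, 1:1. **Assumed:** rescue rates, because none is readable. The plan gives no readable figure for this endpoint to reproduce.

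**Formulas.** Let b(x; n, p) be the binomial probability and F(x, y) the two-sided Fisher p-value for x rescued on placebo and y on octreotide.

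- Size of a rejection set R: the maximum over a common rate p of Σ_R b(x; n₁, p)·b(y; n₂, p), taken on a 2001-point grid.
- Boschloo p-value: the maximum over p of the probability that F is as small as, or smaller than, the observed F.
- Power: Σ_R b(x; n₁, p_placebo)·b(y; n₂, p_octreotide).

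**Why no Fisher rejection is lost.** Given any total, the probability that F ≤ f is at most f under the null. Averaging over totals keeps it at most f. So Boschloo's p-value never exceeds Fisher's.

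**Size, by full enumeration** (arms as placebo/octreotide):

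| Arms | Fisher max size | Boschloo max size | Tables rejected, Fisher → Boschloo |
|---|---|---|---|
| 24/24 | 2.94% | 4.90% | 334 → 354 |
| 25/25 | 3.28% | 4.63% | 362 → 386 |
| 24/26 or 26/24 | 3.74% | 4.81% | 378 → 392 |
| 26/26 | 2.80% | 4.85% | 394 → 424 |
| 27/27 | 2.63% | 4.46% | 424 → 460 |
| 28/28 | 2.77% | 4.62% | 464 → 502 |

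No Fisher rejection is lost in any row. At 25/25, Fisher's size is 3.28% at a common rate of 50%, 2.2% at 20% and 0.9% at 10%.

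**Power at 25/25** (assumed rates):

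| Placebo v octreotide | Fisher | Boschloo | Gain, points |
|---|---|---|---|
| 60 v 25% | 65.4% | 69.5% | 4.0 |
| 50 v 20% | 51.0% | 60.6% | 9.6 |
| 45 v 15% | 53.0% | 64.1% | 11.1 |
| 40 v 10% | 59.1% | 69.0% | 9.9 |
| 60 v 30% | 50.6% | 53.5% | 2.9 |
| 70 v 30% | 78.2% | 79.3% | 1.1 |
| 80 v 20% | 99.4% | 99.4% | 0.05 |

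**Other splits, first four rate pairs in the same order:**

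- placebo 24, octreotide 26: gains of 1.3, 2.1, 3.3 and 2.4 points;
- placebo 26, octreotide 24: gains of 4.7, 5.0, 6.6 and 7.0 points;
- 28/28: gains of 8.0, 7.4, 8.5 and 9.7 points.

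**Example.** For 12/25 v 5/25, Fisher p = 0.072 and Boschloo p = 0.040.

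**Interval against Fisher's p-value, 25/25,** for two exact constructions, each inverted at 2.5% per side:

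- *Score-based exact interval.* In 14 tables per direction of effect (28 in all), the interval excludes zero while Fisher is not significant. For 10/25 v 3/25, p = 0.0507 and the lower limit is about +0.025. The chance of such a conflict is about 9.6% at 50 v 20%.
- *Unstandardised exact interval.* In 10 tables per direction the conflict reverses. For 7/25 v 0/25, p = 0.0096 but the lower limit is about −0.015. The chance is about 8.9% at 40 v 10%, and 0.6% at 50 v 20%.

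**Does changing only the test remove the conflict?** No. The score-based interval excludes zero in 28 tables where Fisher is not significant, but Boschloo adds only 386 − 362 = 24 rejections. So 28 − 24 = 4 discordant tables remain at 25/25. For 4/25 v 0/25, Boschloo p = 0.065 while that interval excludes zero. At 24/26 and at 26/26, 8 discordant tables remain, 4 in each direction. At 26/26, 13 v 6 gives Boschloo p = 0.048 with an interval that includes zero.

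**The case against.** The strongest reply is that the plan contains no error. Fisher's test is valid, both documents name it consistently, and it is exact and conditional, like the exact logistic regression used for the primary and GH endpoints. Choosing another valid exact test is a matter of efficiency. This stands, and it limits the severity.

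A second reply is that the consequence is small. Rescue comes last, is confirmatory only after four other successes, and gates nothing. This also stands. The gain in confirmatory success cannot exceed the gains tabulated above, because a table that only Boschloo rejects counts only when all four earlier tests have passed.

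A third reply is that the disagreement with the interval can be settled while keeping Fisher, by naming the interval method and saying that the p-value decides. That is true, and it is the minimum needed. It leaves the conservatism untouched.

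A reader might go further and infer that Fisher's test always costs 4 to 11 points here. The documents do not support this: they give no readable rates, and the gain is near zero at 80 v 20% and 1 to 3 points at one 24/26 allocation. Nor is 3.3% a general ceiling on Fisher's size; it belongs to 25/25, and the figure is 3.7% at 24/26.

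**Conclusion.** The point holds as a minor improvement in efficiency and specification. At every split checked, Boschloo's test keeps its size below 5%, loses no Fisher rejection and adds some. The power gain is conditional: about 4 to 11 points at 25/25 if placebo rescue is 40% to 60% and octreotide rescue 10% to 25% in the pairs shown, and from about 3 points down to nothing in the other pairs. It also depends on the realised split.

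The firmest part needs no assumed rate: the exact interval has no named method, and the choice of method decides whether, and in which direction, it can contradict the p-value. A reader might expect the conflict always to be an interval excluding zero beside a non-significant p-value. That needs the score-based construction, which the SAP does not specify; the unstandardised one gives the reverse.

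Nothing here suggests an inflated type I error, and no conclusion on the primary endpoint is affected.

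**What to change.** Before unblinding, make these changes for endpoint 4 in SAP 6.8.2, and align Protocol 8.4.4 and the synopsis:

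1. Name Boschloo's exact unconditional test, ordered by the two-sided Fisher p-value, as the confirmatory test.
2. Obtain the 95% interval for the difference by inverting that same test. Write down the ordering used at non-zero differences, since naming the test settles only the zero-difference case. Check once, by enumeration at the realised arm sizes, that the interval excludes zero exactly when the test rejects. A score-based exact interval would not meet this.
3. State that the p-value decides.
4. Report Fisher's p-value as a sensitivity result.

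If Fisher's test is kept as the confirmatory test, still name the interval method and state that the p-value decides.

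The cost is a few lines of text and some programming; no patients or data are added. The downside is that Boschloo's test is less familiar to readers than Fisher's.

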## 6.9 Safety Analyses

All safety analyses for data collected during the DPC period will be presented using the safety set. All safety analyses for data collected during the OLE will be presented using the OLE set (summaries by treatment group will be based on the treatment group in the DPC period). Safety analyses for the DPC period will only use data collected during the DPC period, and will exclude any safety data that was collected after a subject had discontinued study drug. Safety analyses for the OLE will include data collected during the OLE. No formal hypothesis testing will be conducted. Data will be summarized using appropriate descriptive statistics. Missing data will be maintained as missing, unless indicated.

### 6.9.1 Study Drug Exposure and Compliance

#### 6.9.1.1 DPC period

Octreotide capsules can be up-titrated during the DPC period from 40 mg/day to 60 mg/day and 60 mg/day to 80 mg/day, based on clinical and biochemical response.

In the DPC period, the duration of study drug exposure (in days) will be summarized by the treatment group and overall, using descriptive statistics. Duration of study drug exposure will be calculated as date of last dose in the DPC period – date of first dose in the DPC period + 1.

Descriptive statistics for the time to the first dose escalation from 40 mg to 60 mg and time to the second dose escalation from 60 mg to 80 mg will also be presented by treatment group. A figure depicting the time to each dose escalation for each patient will be presented

The number and proportion of patients at each dose level (40, 60 and 80 mg/day) at the end of the DPC period, will also be presented by treatment group.

Compliance to each dose level of octreotide capsules from first dose in the DPC period through the last visit of the DPC period will be calculated and summarized by treatment group overall, and also by the final target dose level achieved within each treatment group.

For the purpose of analysis, compliance to each dose level during the DPC period will be calculated as  $100 \times (\text{total number of capsules actually taken} / \text{total number of capsules expected to be taken})$ . This calculation will be used for each dose level the patient received during the DPC period. The numbers and percentages of patients <75% compliant, 75-100% compliant, and >100% compliant will be tabulated.

The number of actual capsules taken for each dose level will be the total number of capsules dispensed – total number of capsules returned during the time the patient was on that particular dose.

The number of expected capsules taken for the target dose level will be derived as follows:

Dose Level	Expected Number of Capsules Taken
40 mg	2 capsules $\times$ (first day of the phase – last day of the phase)
60 mg	3 capsules $\times$ (first day of the phase – last day of the phase)
80 mg	4 capsules $\times$ (first day of the phase – last day of the phase)
Overall	Sum of expected number of capsules taken over all of the dose levels assigned

A summary of the number of patients who re-initiated SRL treatment in the DPC period will also be provided and will show the number of patients who re-initiated SRL treatment by time point and treatment arm.

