### **6.4.2 Protocol Violations and Treatment Compliance**

For the FAS set, all major protocol violations (e.g., administration of a prohibited concomitant medication, violation of inclusion/exclusion criteria) will be listed by site, including action taken (e.g. discontinuing a subject), if any.

A tabular summary of all major protocol violations will be provided by site, and overall, by treatment group and overall. Major protocol violations will be classified as:

- Violations of inclusion and exclusion criteria
- Receiving the wrong study medication
- Non-compliance with study medication. A patient is defined as non-compliant if the patient took < 75% of the study medication.
- Taking a prohibited medication or receiving a prohibited therapy
- Other

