### **6.9.1.2 OLE Phase**

Octreotide capsules can be up-titrated or down titrated during the OLE. All patients will start on 60 mg/day and can either down titrate to 40 mg/day or up titrate to 80 mg/day, based on clinical and biochemical response.

In the OLE, the duration of study drug exposure (in days) will be summarized by the treatment group and overall, using descriptive statistics. Duration of study drug exposure will be calculated as date of last dose in the OLE– date of first dose in the OLE + 1.

The number and proportion of patients at each dose level (40, 60 and 80 mg/day) at the end of the OLE, will also be presented by treatment group and overall.

Compliance to each dose level of octreotide capsules from first dose in the OLE through the last visit of the OLE will be calculated and summarized by treatment group and overall, and also by the final target dose level achieved within each treatment group during the OLE.

For the purpose of analysis, compliance to each dose level during the OLE will be calculated as  $100 \times (\text{total number of capsules actually taken} / \text{total number of capsules expected to be taken})$ . This calculation will be used for each dose level the patient received during the OLE. The numbers and percentages of patients <75% compliant, 75-100% compliant, and >100% compliant will be tabulated.

The number of actual capsules taken for each dose level will be the total number of capsules dispensed – total number of capsules returned during the time the patient was on that particular dose.

The number of expected capsules taken for the target dose level will be derived as follows:

Dose Level	Expected Number of Capsules Taken
40 mg	2 capsules × (first day of the phase – last day of the phase)
60 mg	3 capsules × (first day of the phase – last day of the phase)
80 mg	4 capsules × (first day of the phase – last day of the phase)
Overall	Sum of expected number of capsules taken over all of the dose levels assigned

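### The expected-capsules formula in SAP 6.9.1.1 and 6.9.1.2 subtracts the last day from the first, so compliance as written is negative for every patient who took capsules and has a defined value

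*SAP*

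**What the plan says.** SAP 6.9.1.1 defines compliance at each dose level as 100 times capsules taken over capsules expected. Capsules taken are those dispensed less those returned while the patient was at that dose. Capsules expected at 40, 60 and 80 mg are 2, 3 or 4 capsules multiplied by ("first day of the phase – last day of the phase"). The Overall row is the "Sum of expected number of capsules taken over all of the dose levels assigned". SAP 6.9.1.2 repeats the same table for the OLE.

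The results are then banded: "The numbers and percentages of patients <75% compliant, 75-100% compliant, and >100% compliant will be tabulated".

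Both sections write exposure the other way round and with one day added: "date of last dose in the DPC period – date of first dose in the DPC period + 1" for the DPC period and "date of last dose in the OLE– date of first dose in the OLE + 1" for the OLE.

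The period covered by compliance is given as "from first dose in the DPC period through the last visit of the DPC period" and, for the extension, "from first dose in the OLE through the last visit of the OLE".

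Separately, SAP 6.4.2 sets a threshold for major protocol violations: "A patient is defined as non-compliant if the patient took < 75% of the study medication". It cites no formula.

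**The concern.** Followed literally, the denominator of the compliance percentage has the wrong sign. Patients with a defined value who took any capsules would all be tabulated as less than 75% compliant, and the more capsules a patient took, the lower the score would be. The tables would say nothing usable about adherence in either period.

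A programmer would notice, but leaving the repair to programming has two drawbacks. SAP Section 1 requires departures from the SAP in the final analysis to be documented in the study report, so a silent repair would be an undocumented departure. The obvious repair, swapping the two dates, is also incomplete: on inclusive day counting it puts fully adherent patients in the >100% band.

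**Working it through.** **Inputs.** The daily capsule numbers (2, 3, 4) and the formula come from the tables in SAP 6.9.1.1 and 6.9.1.2. The DPC length is 36 weeks (protocol synopsis), and 36 x 7 = 252 days. The documents give no numerical compliance result, so there is no stated figure to reproduce. Days are numbered from 1 and counted inclusively. The 336-day OLE phase (48 x 7) and the titration dates are assumptions for illustration.

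**1. Sign of the expression.** With c capsules a day and a phase of L days:
- as written: c x (first - last) = -c x (L - 1)
- order reversed only: c x (last - first) = c x (L - 1)
- exposure convention: c x (last - first + 1) = c x L

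The first is zero at L = 1, where compliance is undefined, and negative at every L above 1.

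**2. As written, single dose level.**
- DPC, 252 days at 2/day: expected 2 x (1 - 252) = -502. Full adherence: 504 / -502 = -100.4%. Half adherence: 252 / -502 = -50.2%. The better adherer scores lower.
- OLE, 336 days at 3/day: expected 3 x (1 - 336) = -1005. Full adherence: 1008 / -1005 = -100.3%.

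**3. As written, Overall row.** Assumed titration: days 1-56 at 2/day, 57-112 at 3/day, 113-252 at 4/day.
- Taken: 112 + 168 + 560 = 840
- Expected: 2 x (1 - 56) + 3 x (57 - 112) + 4 x (113 - 252) = -110 - 165 - 556 = -831
- Compliance: 840 / -831 = -101.1%

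Summing over dose levels does not repair the sign.

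**4. Which repair is sufficient.** Full adherence at 2/day:

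| Phase length | Taken | As written | Reversed only | With +1 |
|---|---|---|---|---|
| 14 days | 28 | 28 / -26 = -107.7% | 28 / 26 = 107.7% | 28 / 28 = 100.0% |
| 28 days | 56 | 56 / -54 = -103.7% | 56 / 54 = 103.7% | 56 / 56 = 100.0% |
| 252 days | 504 | 504 / -502 = -100.4% | 504 / 502 = 100.4% | 504 / 504 = 100.0% |

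The percentages are the same at 3 and 4 capsules a day, because c cancels. Without the +1, full adherence always falls in the >100% band, and the excess is largest for short phases. The 75% boundary also moves: true adherence of 75 x 27/28 = 72.3% reads as 75% over 28 days, and 75 x 251/252 = 74.7% reads as 75% over 252 days. For the titrated patient, the +1 form gives 840 / 840 = 100.0%.

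**The case against.** The strongest case on the other side is that this is a typographical slip that cannot survive programming. The intended order is evident from the exposure formulas nearby, the three bands presuppose non-negative values, and nobody would report -100.4%. That stands as an argument about weight and is why the point is minor. It does not make the printed rule right, and it does not settle the day count.

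The dash might also be read as marking a span of days and not a subtraction. That reading is weak: the same section uses the dash for subtraction in the exposure formula and in capsules dispensed less returned.

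Two exceptions to the negative sign stand. A patient who took no capsules in a phase scores 0%, and a one-day phase has no defined value.

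A reader might infer that the per-protocol set would be emptied, since non-compliance below 75% is a major violation and excludes a patient from that set. The documents do not support this as a finding: SAP 6.4.2 gives neither a formula nor a reference to 6.9.1, so the link is conditional.

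A reader might also infer that the corrected formula must run to the last visit for patients who stop treatment early. The SAP leaves that open. The compliance window runs through the last visit of the period, but capsules taken are counted over the time at a given dose, and SAP 6.9 excludes safety data collected after study drug is stopped from the DPC safety analyses. The choice matters: full adherence at 2/day for 84 days gives 168 / 504 = 33% if expected capsules run through 252 days, and 168 / 168 = 100% if they stop at the last dose. It is a separate question from the sign.

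**Conclusion.** The point holds as a minor error of wording in a stated analysis rule. All six dose-level rows have the subtraction reversed, the Overall rows inherit it, and nothing in the protocol or SAP corrects the sign. Under the literal rule, every patient who took capsules and has a defined value is placed in the <75% band. Full adherence scores about -100%: -100.4% for 252 days at one dose level, and -101.1% in the titrated illustration.

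The effect is confined to the descriptive compliance tables for the two periods. Any effect on the per-protocol set depends on an unstated link to SAP 6.4.2, and that set is only supportive (SAP 6.8.1). The primary analysis uses all randomized patients and does not depend on compliance percentages.

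The sign result needs no assumption beyond reading the dash as subtraction. The case for the +1 assumes that the first and last days of a phase are both counted as full dosing days, which is the convention of the SAP's own exposure formulas.

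**What to change.** In the tables of SAP 6.9.1.1 and 6.9.1.2, replace the bracketed expression in each dose-level row with (last day - first day + 1), multiplied by 2, 3 or 4 capsules as now. Add one sentence that defines a phase as the days assigned to one dose level and assigns each day to one level only, so that days of dose change are not counted twice.

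As a separate matter, before unblinding, the sponsor should reconcile the through-last-visit window with the time-at-dose count of capsules taken and with the post-discontinuation exclusion in SAP 6.9, and state when the last phase ends for early discontinuers. The correction above prescribes neither answer. Optionally, SAP 6.4.2 could name the compliance figure to which its 75% rule applies.

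The cost of the correction is SAP wording only: six table rows and one sentence. Endpoints, analysis sets and data collection do not change.
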